5.5.3. Intrahepatic Immune and Viral Parameters at FU Week 24 (Week 72)

For all participants with biopsy data available at FU Week 24, the same analyses as described in Sections 5.3.1.2.3, 5.4.1.1 and 5.4.1.2 may be performed. Graphs over time will display baseline, Week 40 and FU Week 24 data.

5.5.4. Liver Stiffness Measurement (LSM)

The proportion of participants with the following LSM changes from baseline (both in terms of reductions and increases) will be evaluated over time at Week 48, FU Week 24 and FU Week 48 /EOS:

- ≥ 1 kPa
- ≥ 2 kPa
- ≥ 4 kPa
- ≥ 6 kPa

Only participants from sites with available VCTE (Fibroscan) will be included in the analysis. Within these participants, missing LSM (in kPa) at a specific timepoint will be considered as non-responders for that timepoint. No imputation rule will be used in case of missing data.

In addition, the change from baseline in LSM will be compared between study panels at Week 48 using ANCOVA with study panel as main effect in the model and baseline score as covariate.

At each assessment time point, a frequency distribution of severity scores will be produced. A graphical display will also illustrate the findings. In addition, a waterfall plot will be produced to display the individual changes from baseline in LSM.

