
 To explore changes in the severity of liver disease 	
 Changes in fibrosis (according to Fibroscan liver stiffness measurements) at the end of study intervention (EOSI) and end of follow-up versus screening/baseline*

 To explore the efficacy in terms of changes in HBV RNA and hepatitis B core-related antigen (HBcrAg) levels. 	
 Changes from baseline in HBV RNA and HBcrAg levels during study intervention and follow-up phases.

 To explore the relationship between plasma PK parameters (JNJ-3989 [i.e., JNJ-3976 and JNJ-3924] and/or JNJ-6379 and/or NA and/or PegIFN-α2a) and selected pharmacodynamic (PD) parameters of efficacy and/or safety, as applicable 	
 Relationship between various plasma PK parameters (JNJ-3976 and JNJ-3924, and/or JNJ-6379, and/or NA, and/or PegIFN-α2a) and selected efficacy and/or safety endpoints, as applicable

 To explore the HBV genome sequence 	
 The emergence of intervention-associated mutations during the study intervention and follow-up phases To assess the impact of baseline HBV genome polymorphisms on selected on/off-treatment efficacy variables

* Only applicable to participants who are enrolled at a site with an on-site Fibroscan device.

1.1.2. For Panel 3

An additional single-arm Panel 3 will be enrolled to assess liver concentrations of JNJ-3989, i.e., JNJ-73763976 (JNJ-3976), JNJ-73763924 (JNJ-3924), and JNJ-87719164 (also known as M65, a deaminated metabolite of JNJ-3976) in HBV-infected participants.

The following objectives and endpoints will be assessed for Panel 3:

Objectives (Panel 3)	Endpoints (Panel 3)
Primary*	

 To assess changes in drug concentrations over time during JNJ-3989-based combination treatment 	
 Liver concentrations of JNJ-3989 (i.e., JNJ-3976 and JNJ-3924)* measured at treatment Weeks 12 and 40 Assessment of drug accumulation in the liver over time Correlation of liver and plasma PK levels
Secondary	

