1.2. Study Design

A target of 24 chronic HBV-infected male and female participants, 18-65 years (inclusive) of age

will be enrolled in Panels 1 and 2, approximately 12 participants in each panel. In Panel 3, a target of 4-6 chronic HBV-infected male and female participants will be enrolled.

- Panel 1 will consist of participants who are HBeAg positive and not currently treated.
- Panel 2 will consist of participants who are HBeAg negative and virologically suppressed by ETV, TD, or TAF treatment.
- Panel 3 will consist of participants who are HBeAg positive or negative and are either not currently treated or virologically suppressed by ETV or TD treatment.

The study will be conducted in 3 phases for all participants:

- A **screening phase** (4 to 6 weeks),
- An **open-label study intervention phase** (48 weeks),
- A **follow-up phase** (48 weeks). Note that the follow-up period will be extended up to an additional 24 weeks for participants who are receiving optional treatment with PegIFN- α 2a and who meet NA treatment completion criteria at the end of treatment with NA and PegIFN- α 2a to ensure all participants have at least one year of follow-up after NA treatment cessation.

The duration of individual participation will be up to 102 weeks for participants who stop NA treatment at the end of the open-label phase, or up to 126 weeks for participants who stop NA treatment during the follow-up phase.

Prior to Protocol Amendment 5, in Panels 1 and 2, participants were randomized in a 1:1 ratio within each panel to receive one of the following interventions (i.e., treatments) for 48 weeks:

- **Arm 1**, combination regimen JNJ-3989+JNJ-6379+NA:
 - 200 mg JNJ-3989 (SC injection Q4W, with the last injection at Week 44), and
 - 250 mg JNJ-6379 (tablets qd), and
 - NA: ETV, TD, or TAF (tablets qd)
- **Arm 2**, combination regimen JNJ-3989+NA:
 - 200 mg JNJ-3989 (SC injection Q4W, with the last injection at Week 44), and
 - NA: ETV, TD, or TAF (tablets qd).

As of Protocol Amendment 5, in Panels 1 and 2, participants who were previously randomized to Arm 1 had to stop JNJ-6379 treatment immediately but will still receive JNJ-3989 and NA – effectively joining Arm 2. New participants will enroll without randomization to Arm 2.

No participants were enrolled in Panel 3 before Protocol Amendment 5 was in effect. Therefore, all Panel 3 participants will enroll without randomization to receive the Arm 2 regimen.

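### SAP 5.5.4 counts a missing liver stiffness scan as a non-responder for increases as well as reductions; read literally, the reported proportion with an increase is the lowest the data allow

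*SAP*

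**What the plan says.** The exploratory objective is neutral as to direction: "To explore changes in the severity of liver disease" (SAP 1.1). SAP 5.5.4 accordingly plans threshold proportions in which "LSM changes from baseline (both in terms of reductions and increases) will be evaluated over time at Week 48, FU Week 24", and also at the Follow-up Week 48/end-of-study visit.

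The denominator is set by site: "Only participants from sites with available VCTE (Fibroscan) will be included in the analysis". Within that group, "missing LSM (in kPa) at a specific timepoint will be considered as non-responders for that timepoint". The rule is not split by direction, and the section does not define a responder for an increase. The sentence that follows reads "No imputation rule will be used in case of missing data".

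The section then adds an ANCOVA of change at Week 48 between panels, a frequency distribution of severity scores, and a display of individual values: "In addition, a waterfall plot will be produced to display the individual changes from baseline in LSM". Neither document gives a separate missing-data rule for LSM increases.

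**The concern.** Scoring missing as non-response is a convention for favourable outcomes, where it guards against overstating benefit. Applied to an unfavourable outcome it works the other way. In an increase row, a non-responder is someone who did not increase, so an absent scan lowers the reported proportion. A participant with no scan then appears in neither the reduction rows nor the increase rows and is in effect treated as stable.

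The following sentence adds a second difficulty. If it means observed cases, the denominator changes and the non-responder rule has no effect. Two programmers following the same section could produce different tables.

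What is at stake is the interpretation of a small descriptive table. A reader comparing reductions with increases would not know that the increase column is a floor.

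**Working it through.** **No plan figure to reproduce.** The documents state no LSM rate, LSM sample size or LSM missingness. The check is direct arithmetic under labelled assumptions.

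**Inputs**
- *N*, participants at Fibroscan sites: not given. The target for Panels 1 and 2 is 24 (SAP 1.2), used here as a ceiling for those panels.
- *m*, participants without a usable LSM at the visit: not given. SAP Section 3 assumes a 20% drop rate for sample size; applying it to LSM is an assumption. Rounded on 24, missingness of 10%, 20% and 30% gives 2, 5 and 7.
- *k*, participants measured as increased: 4, assumed.

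**Formulas**
- SAP rule read literally: k / N
- Observed cases: k / (N − m)
- All missing counted as increased: (k + m) / N

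The proportion among all N must lie between the first and third expressions, so the literal rule always reports the bottom of the range.

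| Missing (m) | SAP rule | Observed cases | Missing counted as increased |
|---|---|---|---|
| 2 | 4/24 = 16.7% | 4/22 = 18.2% | 6/24 = 25.0% |
| 5 | 4/24 = 16.7% | 4/19 = 21.1% | 9/24 = 37.5% |
| 7 | 4/24 = 16.7% | 4/17 = 23.5% | 11/24 = 45.8% |

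With no missing scans, all three agree.

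**Expected understatement.** Let p be the rate of increase among those measured and f the missing fraction. The SAP rule reports p(1 − f).
- If missing participants increase at the same rate, the true rate is p. The relative understatement is f: 10%, 20% or 30%.
- If they increase at twice the rate (an assumption), the true rate is p(1 − f) + 2pf = p(1 + f). The relative understatement is 1 − (1 − f)/(1 + f): 18%, 33% or 46%.
- In that second case observed cases are also low, by 1 − 1/(1 + f). At f = 0.2 this is 1 − 1/1.2 = 17%.

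**Comparison with other SAP rules.** Functional cure (5.4.2.5) scores missing as non-response, which fits a favourable outcome. Virologic flare (5.4.2.6.1) gives participants with no off-treatment HBV DNA measurement their own not-applicable code, separate from No. Laboratory abnormalities (5.6.3.1) count as treatment-emergent when the baseline is missing, which errs toward reporting harm. The practice is not uniform, since biochemical flare has only a residual No category, but the SAP does elsewhere distinguish missing from absent.

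**The case against.** **The rule may be meant for reductions only.** A responder is ordinarily someone who improves. That may be the intention, but the text does not say so. The rule follows a sentence that names changes "both in terms of reductions and increases" and carries no restriction.

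**The two sentences can be reconciled.** No imputation may mean that no kPa value is filled in, while the participant still counts in the threshold table. This is reasonable, and the sentence stands directly before the ANCOVA, the severity distribution and the waterfall plot, which need such a statement. It is a reason to scope the sentence rather than delete it. Under this reading, however, the non-responder rule remains in force for increases.

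**Little is hidden.** The count of participants with an increase is the same under either rule; only the denominator moves. The waterfall plot also shows measured increases. Both points stand and limit the importance of the issue, although neither display shows participants with no scan.

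**Stronger readings the documents do not support.** A reader might infer that LSM increase is a harm measure after nucleos(t)ide analog (NA) cessation and that harm is therefore being concealed. The protocol lists Fibroscan under efficacy assessments and the objective is exploratory. Week 48 is the visit at which NA may be completed, not a time after it, and participants who do not meet the completion criteria continue NA in follow-up. Deterioration after stopping NA is followed through liver tests, HBV DNA, the flare analyses and the independent flare panel, none of which uses this rule. A reader might also infer that worsening causes missing scans; nothing in the documents bears on that.

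**Conclusion.** The point holds as a flaw in the wording of SAP 5.5.4. Taken literally, the threshold proportions for LSM increases are lower bounds that are not labelled as such, and the section leaves open whether that rule or observed cases applies. It would go too far to say that deterioration will be under-reported: if the analysts use observed cases, or if no scans are missing, the effect of the rule does not arise.

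In the central illustration the reported 16.7% compares with 21.1% for observed cases, within a possible range of 16.7% to 37.5%. This rests on the assumed denominator, number missing and number increased; the documents supply none of the three for LSM. The primary endpoint, the other safety analyses and the continuous LSM analyses are unaffected. The correction is worth making because the remedy is simple and the table is otherwise ambiguous.

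**What to change.** Reword SAP 5.5.4 so that the missing-data rule is stated by direction.

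- **Reductions:** keep missing as non-response.
- **Increases:** report observed cases, showing the number evaluable and the number missing at each visit. Add a bound that counts every missing participant as increased. The bound is needed because observed cases alone would still be low if missing participants fared worse.
- **No-imputation sentence:** keep it, but say that no kPa value is imputed for the continuous analyses (ANCOVA, severity-score distribution, waterfall plot).

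The two directions will then have different denominators, so both should be printed in the table. The cost is SAP wording and a few extra entries in one table shell. No new data or assessments are needed.

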5.5.5. HBV RNA and HBcrAg

HBcrAg will be summarized by treatment history (not currently treated and virologically suppressed) and overall, while HBV RNA will only be summarized by treatment history.

The values of and changes from baseline in HBV RNA and HBcrAg, respectively, will be summarized only descriptively over time in a similar manner as for values and changes from baseline over time in HBsAg, HBeAg, and HBV DNA as described in Section 5.4.2.4.1, including the change from baseline value to nadir (i.e., maximum decrease for each participant) and the various graphical displays.

Waterfall plots for changes from baseline of HBV RNA and HBcrAg will also be presented.

5.5.6. Sustained HBsAg Response

The definitions of sustained response are as follows:

Definition 1 (yes/no):

- For participants with data at the last scheduled follow-up visit (Follow-up Week 48 for participants who did not receive PegIFN- α 2a or received PegIFN- α 2a and did not meet NA completion criteria, and last Follow-up visit for participants who received PegIFN- α 2a and stopped NA during Follow-up): Participants who have a > 1 log decline in HBsAg at last scheduled follow-up visit and have an HBsAg < 1000 IU/mL at the last scheduled follow-up visit.
- For participants without data at the last scheduled follow-up visit: HBsAg values have a > 2 log decline at the second most recent visit or > 1.5 log decline at the latest visit (most recent value used) compared to baseline and have an HBsAg < 1000 IU/mL at the last available timepoint.

Definition 2 (yes/no): For participants with a > 1 log decline in HBsAg from baseline at last follow-up visit: Among the most recent three visits, the difference between log HBsAg at 2 of 3 last visit and 1 of 3 last visit is < 0.2 , and the difference between log HBsAg at 3 of 3 last visit and 1 of 3 last visit is < 0.2 .

Definition 3 (yes/no): For participants with a > 1 log decline in HBsAg from baseline at last follow-up visit: Among the most recent three visits, the difference between log HBsAg at 2 of 3 last visit and 1 of 3 last visit is < 0.2 , and the difference between log HBsAg at 3 of 3 last visit and 1 of 3 last visit is < 0.2 and have an HBsAg < 1000 IU/mL at the last available timepoint.

Definition 4 (>0.2 log increase, $+/-0.2$ log, >0.2 log decline): Three categories regarding the difference between HBsAg level at the last Follow-up timepoint and EOT:

- $>0.2 \log_{10}$ decrease: Decreasing level
- $\leq 0.2 \log_{10}$ increase or $\leq 0.2 \log_{10}$ decrease: Stable level
- $>0.2 \log_{10}$ increase: Increasing level

Due to the exploratory objectives of this Phase 2 study, additional sustained HBsAg response definitions may be explored according to the clinical interest.

For all definitions of the sustained HBsAg response, only participants with at least 24 weeks after JNJ-3989 stop will be used for the analysis.

The count and proportion (%) of participants achieving sustained HBsAg response will be summarized.

Spaghetti plots for HBsAg actual values and change from baseline will be presented by study panel over time using color coding by category.

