6. Participants must have HBsAg  $>100$  IU/mL at screening.
7. Participants must have a body mass index (weight in kg divided by the square of height in meters) between 18.0 and 35.0 kg/m^2, extremes included.
8. Participants must have fibroscan liver stiffness measurement  $\leq 9.0$  kPa within 6 months prior to screening or at the time of screening.

**Note:** Other radiologic liver staging modalities (eg, acoustic radiation force impulse) might be used if standard practice at the site or if otherwise validated and agreed with the

sponsor. Results should be equivalent to Metavir F0-F2 with absence of signs of portal hypertension.

**Note:** Conventional imaging procedures (eg, conventional liver ultrasound, computed tomography [CT] or magnetic resonance imaging [MRI]) and serum marker panels are not allowed to rule out severe fibrosis or cirrhosis.

9. Female participants of childbearing potential must have a negative highly sensitive serum pregnancy test ( $\beta$ -human chorionic gonadotropin [ $\beta$ -hCG]) at screening and a negative urine pregnancy test on Day 1 before the first dose of study intervention.
10. Criterion modified per Amendment 5

10.1 A woman must be (as defined in Section 10.8, Appendix 8, Contraceptive and Barrier Guidance and Collection of Pregnancy Information):

- a. not of childbearing potential
- b. of childbearing potential and practicing a highly effective, preferably user-independent method of contraception (failure rate of <1% per year when used consistently and correctly) for at least 30 days prior to screening and agrees to remain on a highly effective method while receiving study intervention and until 90 days after last dose of study intervention.

Examples of highly effective methods of contraception are located in Section 10.8, Appendix 8, Contraceptive and Barrier Guidance and Collection of Pregnancy Information.

**Note:** Typical use failure rates may differ from those when used consistently and correctly. Use should be consistent with local regulations regarding the use of contraceptive methods for participants in clinical studies.

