Type of NA at study entry (only for virologically suppressed participants): TD, TAF, ETV	

Continuous Variables	Summary Type
HBV viral activity and serology parameters	Frequency distribution with the number and percentage of participants in each category.
HBeAg status at study entry: positive, negative	
HBsAg category at baseline (IU/mL): < 500, < 1,000, < 10,000, ≥ 10,000	
HBV DNA category at baseline (IU/mL): < LLOQ Target detected (TD) or not detected (TND), < LLOQ TD, < LLOQ TND, < 60, < 2,000, < 20,000, < 100,000, ≥ 100,000	
HBV RNA category at baseline (copies/mL): TND, < Limit of Detection (LOD), < LLOQ, < 1,000, ≥ 1,000	
HBcrAg category at baseline (log U/mL): < 3, ≥ 3 - < 4, ≥ 4	
HBsAg Antibody (Anti-HBs) status at baseline: Positive, Negative	
HBsAg Antibody (Anti-HBs) category at baseline (mIU/mL): < 10, ≥ 10	
HBeAg Antibody (Anti-HBe) status at baseline: Positive, Negative	
Baseline ALT toxicity grade according to DAIDS	
Baseline ALT categorization: ≤ 1.0xULN, > 1.0xULN to <2.5xULN, ≥ 2.5x	
Stage of liver fibrosis: F0, F1, F2	

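### Sustained HBsAg response, Definition 1: without a final visit, a participant can be scored sustained with no decline from baseline required at the latest value

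*SAP*

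**What the plan says.** SAP 5.5.6 gives four definitions of sustained HBsAg response. Definition 1 has two branches.

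- **Final-visit data present.** The branch covers "Participants who have a > 1 log decline in HBsAg at last scheduled follow-up visit" and who have HBsAg below 1000 IU/mL at that same visit. I call this the completer rule.
- **No final-visit data.** The decline test is that "HBsAg values have a > 2 log decline at the second most recent visit or > 1.5 log decline at the latest visit". A parenthesis after the second limit reads "most recent value used". The sentence then ends "compared to baseline and have an HBsAg < 1000 IU/mL at the last available timepoint".

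For all four definitions, "only participants with at least 24 weeks after JNJ-3989 stop will be used for the analysis". Definitions 2 and 3 each require a decline of more than 1 log at the last follow-up visit and close agreement among the last three values.

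Low baselines are expected. Protocol 5.1, criterion 6, begins "Participants must have HBsAg" and sets the limit at more than 100 IU/mL at screening. SAP 6.3.2 tabulates "HBsAg category at baseline (IU/mL): < 500, < 1,000, < 10,000" and upward. SAP Table 6 plans baseline subgroups split at 1000 and at 10,000 IU/mL.

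**The concern.** The limits of 1.5 and 2 log look like stricter substitutes for the 1 log limit, meant to compensate for the missing endpoint visit. Joined by *or*, they do not act that way. Once the older of the two values shows more than 2 log, the newer value faces no decline requirement. The branch is then more lenient than the completer rule in exactly the case where the newer value shows rebound. It is the only route to a Yes under Definitions 1 to 3 that requires no decline from baseline at the latest value.

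According to the SAP version history, the section was added to describe off-treatment HBsAg response better. Counting a rebound as sustained works against that purpose, and it would happen among participants with the shorter record of durability.

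**Working it through.** There is no plan figure to reproduce, so the check applies the written rule to hypothetical profiles.

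**Conditions**, with b = baseline, s = second most recent value and l = latest value, all in IU/mL:

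- A: log10(b/s) > 2
- B: log10(b/l) > 1.5
- C: l < 1000
- Completer rule: log10(b/l) > 1 and l < 1000

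**Three possible readings of the no-final-visit branch:**

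- R1: (A or B) and C. This is the natural reading, because the verb is repeated before the 1000 IU/mL condition.
- R2: A or (B and C).
- R3: B and C, with the parenthesis taken to mean that the most recent value governs throughout.

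| b / s / l | log10(b/s) | log10(b/l) | R1 | R2 | R3 | Completer rule on l |
|---|---|---|---|---|---|---|
| 900 / 8 / 880 | 2.05 | 0.01 | Yes | Yes | No | No |
| 3,000 / 25 / 900 | 2.08 | 0.52 | Yes | Yes | No | No |
| 5,000 / 40 / 950 | 2.10 | 0.72 | Yes | Yes | No | No |
| 5,000 / 40 / 4,500 | 2.10 | 0.05 | No | Yes | No | No |
| 10,000 / 90 / 990 | 2.05 | 1.00 (unrounded 1.004) | Yes | Yes | No | Yes |
| 30,000 / 250 / 990 | 2.08 | 1.48 | Yes | Yes | No | Yes |

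**What condition C forces under R1.** Since l < 1000, the decline at the latest value must exceed log10(b/1000):

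- b = 500: -0.30, so the latest value may even lie above baseline
- b = 1,000: 0
- b = 2,000: 0.30
- b = 5,000: 0.70
- b = 10,000: 1.0

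**Where R1 conflicts with the completer rule.** A decline of 1 log or less means l >= b/10. With l < 1000 this requires b < 10,000. From 10,000 IU/mL upward, R1 is no looser than the completer rule.

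**Where a return to near baseline passes.** A latest value within k log of baseline passes C only if b < 1000 x 10^k. This gives 1,585 IU/mL for k = 0.2 and 1,995 IU/mL for k = 0.3.

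**Size of the rise needed between the last two values.** A decline above 2 log followed by one of 1 log or less is a rise of more than 1 log. In the examples, 5,000/40/950 rises 2.10 - 0.72 = 1.38 log and 900/8/880 rises 2.05 - 0.01 = 2.04 log. Follow-up visits are 4 weeks apart off NA, and may be 12 weeks apart for stable participants on NA (Protocol 1.3.2).

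**The case against.** A reader might infer that the second most recent value suffices by itself, so that any participant back near baseline is counted. The documents do not support that. The same sentence requires the latest value to be below 1000 IU/mL, and on the natural reading this blocks a return to within 0.3 log of baseline once baseline reaches about 2,000 IU/mL. The broad claim holds only under R2, the less natural grouping.

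A reader might also size the branch from the 20% drop rate in SAP section 3 (0.20 x 24 = 4.8 participants). SAP Attachment 1 ties that rate to usable data for the primary analysis, which rests on the Week 40 biopsy. It does not describe loss before Follow-up Week 48, and 5.5.6 already removes anyone with less than 24 weeks after JNJ-3989.

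On intent, the three limits fit a sliding scale: the further the last value lies from the final visit, the larger the decline required, with the most recent value governing. No rebounder passes on that reading (R3). It is plausible, but it leaves the limb on the second most recent visit with no effect, so the text does not establish it.

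On consequence, the endpoint is exploratory and untested. Both 900/8/880 and 5,000/40/950 fail Definitions 2 and 3, Definition 4 reports change since end of treatment, and individual profiles are plotted. Protocol 2.2.2.1 reports mean HBsAg below baseline until about 9 months after the last dose in a substantial proportion of patients, so a rise above 1 log between successive visits looks unusual. These points stand. They limit the impact but do not make the written rule correct.

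**Conclusion.** The rule is wrong as written, with limited impact. On the natural reading, a participant without final-visit data can be scored sustained with no required decline from baseline at the latest value. This can contradict the completer rule only for baselines below 10,000 IU/mL and only after a rise of more than 1 log between the last two values. A return to near baseline can pass only for baselines below about 2,000 IU/mL, after a rise of about 2 log.

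The number affected cannot be computed: the documents give neither a baseline HBsAg distribution nor a rate of missing final visits. The branch covers participants with at least 24 weeks after JNJ-3989 who lack the final visit. That includes people still in follow-up if the definition is applied at the second interim analysis, where SAP Table 7 schedules exploratory endpoints. With 24 participants in Panels 1 and 2, one reclassification moves the rate by 1/24 = 4.2 points, or 1/12 = 8.3 points within a panel; the set analysed may be smaller.

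The conclusion rests on reading R1. That three readings give different answers for the same participant is itself a reason to rewrite a programmed yes/no definition.

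**What to change.** For participants without data at the last scheduled follow-up visit, classify on the latest available value only: a decline from baseline of more than 1.5 log and HBsAg below 1000 IU/mL, both at that value. Delete the alternative based on the second most recent visit. If a stricter limit is wanted when data end two or more scheduled visits early, apply the limit of more than 2 log to that same latest value.

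The cost is one line of SAP text and the matching program line. The reported rate may be slightly lower. Some participants whose latest decline lies between 1 and 1.5 log, such as 10,000/90/990 and 30,000/250/990, would change to No although the completer rule would accept that value. That follows from keeping the SAP's own 1.5 log limit for missing final visits.
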